4.3.1.3.3 Unsolicited Non-serious Adverse Events From D0 to V02 After Vaccination

In addition to recording solicited reactions, subjects or subjects' parents/guardians will be instructed to record any other medical events that may occur between V01 and V02. Space will be provided in the DC for this purpose. For each unsolicited non-serious AE, the following information is to be recorded:

- Start and stop dates⁷
- Intensity of the event:
 - For measurable unsolicited non-serious AEs that are part of the list of solicited reactions, the size of the AE as well as the temperature for fever will be collected and analyzed based on the corresponding scale used for solicited reactions (see Table 4.1 and Table 4.2).

⁶ Regardless of the arm circumference measurements and differences, if in the subject's or subject and their parent/guardian opinion the subject develops ELS of the vaccinated arm during the 7 day period after vaccination, the subject or subject and their parent/guardian is required to contact the site immediately on the same day the ELS is observed

⁷ The stop date of all related AEs will be actively solicited. For other events, the investigator will provide the stop date when it becomes available. AEs for which no stop date was obtained during the course of the study will be considered as ongoing at the end of the study.

- Other unsolicited non-serious AEs will be classified according to the following intensity scale:
 - Grade 1: No interference with activity
 - Grade 2: Some interference with activity
 - Grade 3: Significant; prevents daily activity
- Action taken for each AE, if any (e.g., medication)

The action taken by the subjects or subjects' parents/guardians to treat any **unsolicited AEs** will be classified in the eCRF using the following scale:

- 0: None
 - 1: Medication (self-medication with an existing prescription or over-the-counter medication)
 - 2: Health care provider contact (no new medication prescribed)
 - 3: Health care provider contact and prescription of a new medication (health care provider instructed subject to take a new medication, either an over-the-counter medication or one requiring a written prescription)
- Whether the AE led to discontinuation
 - Whether the AE was related to vaccination (for unsolicited systemic AEs)

4.3.1.3.4 Serious Adverse Events

Information on SAEs will be collected and assessed throughout the trial, from inclusion until 6 months after vaccination.

Any SAE occurring at any time during the trial will be reported by the Investigator through the EDC system and according to the completion guidelines provided by the Sponsor. All information concerning the SAE is to be reported, either as part of the initial reporting or during follow-up reporting if relevant information became available later (e.g., outcome, medical history, results of investigations, copy of hospitalization reports). The Investigator will assess the causal relationship between the SAE and the investigational product as either "Not related" or "Related", as described in Section 4.3.1.3.7.

4.3.1.3.5 Adverse Events of Special Interest

No Adverse Events of Special Interest will be assessed in this study.

4.3.1.3.6 Medically Attended Adverse Events

MAAEs that occur from V01 (D0) to V02 will be recorded as unsolicited AEs on the DC as part of the unsolicited AEs collected for this post-vaccination period. MAAEs that occur from V02 to the long-term safety phone call at approximately 6 months after vaccination will be recorded as such in the MA. An MAAE that occurs within the study but meets the definition of an SAE should be reported only on the SAE reporting form.

4.3.1.3.7 Assessment of Causality

The Investigator will assess the *causal relationship* between each unsolicited systemic AE and vaccination as either not related or related, based on the following definitions⁸:

- 0: Not related – The AE is clearly / most probably caused by other etiologies such as subject’s underlying condition, therapeutic intervention, or concomitant therapy; or the delay between vaccination and the onset of the AE is incompatible with a causal relationship; or the AE started before the vaccination (screening phase, if applicable)
- 1: Related – There is a “reasonable possibility” that the AE was caused by the vaccination, meaning that there is evidence or arguments to suggest a causal relationship

Note: By convention, all injection site AEs (solicited and unsolicited) and all solicited systemic reactions are considered to be related to vaccination and referred to as reactions, and therefore do not require the Investigator’s opinion on relatedness.

AEs likely to be related to the product, whether serious or not, that persist at the end of the trial will be followed up by the Investigator until their complete disappearance or the stabilization of the subject’s condition. The Investigator will inform the Sponsor of the date of final disappearance of the event.

4.3.2 Immunogenicity

4.3.2.1 Immunogenicity Endpoints

- Anti-pertussis (PT, FHA, PRN, and FIM) antibody concentrations pre- and post-vaccination measured by enzyme-linked immunosorbent assay (ELISA)
- Anti-diphtheria antitoxin concentration pre- and post-vaccination assessed by toxin neutralization assay
- Anti-tetanus antitoxin concentration pre- and post-vaccination measured by ELISA

4.3.2.2 Immunogenicity Assessment Methods

Anti-Bordetella pertussis Antibodies

Assays will be performed by ELISA at Sanofi Pasteur. Purified PT, FHA, PRN, or FIM 2&3 antigen is adsorbed to the wells of a microtiter plate. Diluted serum samples (test samples, reference standards, and quality controls) are incubated in the wells. Specific antibodies in the serum samples bind to the immobilized antigen to form antigen-antibody complexes. Unbound antibodies are washed from the wells, and enzyme-conjugated anti-human immunoglobulin (IgG) is added. The enzyme conjugate binds to the antigen-antibody complex. Excess conjugate is washed away and a specific colorimetric substrate is added. Bound enzyme catalyzes a hydrolytic reaction causing color development. The intensity of the generated color is proportional to the amount of specific antibody bound to the wells. The results are read on a spectrophotometer

⁸ ICH Guidelines, Clinical Safety Data Management E2A

(ELISA plate reader). An in house reference standard serum assayed on each plate is used to calculate the amount of specific PT, FHA, PRN, or FIM 2&3 antibody in the test samples in ELISA units per milliliter (EU/mL) by comparison to the reference standard curves. The lower limit of quantitation (LLOQ) for the anti-PT, PRN, and FIM ELISA is 4 EU/mL and the LLOQ for the anti-FHA ELISA is 3 EU/mL.

Antibodies to Tetanus Toxin

Assays will be performed by ELISA at Sanofi Pasteur. Purified tetanus toxoid is adsorbed to the wells of a microtiter plate. Diluted serum samples (test samples, reference standard, and quality control) are incubated in the wells. Specific antibodies in the serum samples bind to the immobilized antigen. Unbound antibodies are washed from the wells, and enzyme-conjugated anti-human immunoglobulin (IgG) is added. The enzyme conjugate binds to the antigen-antibody complex. Excess conjugate is washed away and a specific colorimetric substrate is added. Bound enzyme catalyzes a hydrolytic reaction, which caused color development. The intensity of the generated color is proportional to the amount of specific antibody bound to the wells. The results are read on a spectrophotometer (ELISA plate reader). A reference standard assayed on each plate, WHO human standard lot TE3, is used to calculate the amount of specific anti-tetanus antibody in the unitage assigned by the reference standard (IU/mL of serum). The LLOQ for the anti-tetanus ELISA is 0.01 IU/mL.

Antibodies to Diphtheria Toxin

Assays are performed by a toxin neutralization test at Sanofi Pasteur. Serial dilutions of human sera are mixed with diphtheria challenge toxin and incubated with Vero cells that are sensitive to the toxin. Neutralizing antibodies specific to diphtheria toxin contained in the serum samples bind to and neutralize the toxin. The neutralized toxin does not affect cellular viability, therefore the cultured cells continue to metabolize and release carbon dioxide (CO₂), reducing the pH of the culture medium. Cell survival correlates with the change in the color of the pH indicator (phenol red to yellow at pH ≤ 7.0) contained in the medium. In the absence of neutralizing antibodies, the challenge toxin reduces cellular metabolism and CO₂ production, therefore the pH does not decrease and a color change is not detected. The LLOQ is 0.005 IU/mL.

4.3.3 Efficacy

No clinical efficacy data will be obtained in the trial.

4.4 Derived Endpoints: Calculation Methods

4.4.1 Safety

4.4.1.1 Solicited Reactions

4.4.1.1.1 Daily Intensity

All daily records for solicited reactions will be derived into daily intensity according to the following classification: None, Grade 1, Grade 2, Grade 3, or Missing.

Note: all instances of extensive limb swelling will be considered a Grade 3 reaction.

For the derivation of daily intensities the following sequential steps will be applied:

- 1) Solicited reactions (except Fever/Pyrexia) with an investigator presence recorded as “No” and with all daily records missing then all daily intensities will be derived as None.
- 2) For non-measurable solicited reactions, daily intensities will correspond to daily records reported in the clinical database. For measurable solicited reactions the daily measurements reported in the clinical database will be converted based upon the intensity scales defined in the protocol; this assumes a reaction that is too large to measure (non measurable, “NM”) is Grade 3. Note the intensity could be considered “None” (not a reaction) in the analysis despite being considered a reaction by the investigator (e.g., swelling measurement > 0 mm but < 25 mm in adults).

Note: The maximum intensity on the ongoing period is derived from the record of the maximum intensity/measurement after the end of the solicited period following the rule described above.

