4.4.1.1.3 Presence

Presence is derived from the maximum overall intensity on the period considered:

- None: No presence
- Grade 1, Grade 2, or Grade 3: Presence
- Missing: Missing presence

Subjects with at least one non-missing presence for a specific endpoint will be included in the analysis. Conversely, those without a non-missing presence will not be included in the analysis of the endpoint.

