5.3 Handling of Missing Data and Outliers

5.3.1 Safety

No replacement will be done. All subjects with safety data and all safety data recorded in the eCRFs will be included in the safety analyses.

In all subject listings, partial and missing data will be clearly indicated as missing.

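### For solicited reactions other than fever, a subject with no daily records is kept if the investigator recorded No and excluded if the investigator recorded Yes, so any-grade rates for pain, headache, malaise and myalgia can only be understated

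*SAP*

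**What the plan says.** SAP 4.4.1.1.1 classifies each daily record for a solicited reaction "according to the following classification: None, Grade 1, Grade 2, Grade 3, or Missing". The derivation runs in sequence.

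- **Step 1** applies to "Solicited reactions (except Fever/Pyrexia) with an investigator presence recorded as" No. For such a reaction "with all daily records missing then all daily intensities will be derived as None". Fever is outside this step.
- **Step 2** takes intensity from the daily data alone: "For non-measurable solicited reactions, daily intensities will correspond to daily records reported in the clinical database". For measured reactions, the daily measurement is converted to a grade.

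Neither step mentions a Yes with no daily records. SAP 4.4.1.1.2 takes the maximum of the daily intensities. In SAP 4.4.1.1.3, "Presence is derived from the maximum overall intensity on the period considered", and a Missing maximum gives missing presence. The consequence is stated there: "Conversely, those without a non-missing presence will not be included in the analysis of the endpoint".

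SAP 5.3.1.4 sends missing solicited intensities back to 4.4.1.1.1 and adds no rule. SAP 5.3.1 says that nothing will be replaced, and also that "All subjects with safety data and all safety data recorded in the eCRFs will be included in the safety analyses".

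**The concern.** The investigator's presence field is used when it says No and ignored when it says Yes. Take two subjects with no daily pain entries. The one whose site record says no pain is counted as a zero. The one whose site record says pain was present leaves both numerator and denominator. Whether a subject is analysed depends on the result being measured.

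Describing the safety profile of each formulation is one of the trial's two objectives, and Protocol 1.4 makes safety data a determinant of which formulation advances. For the terms where the direction is fixed, the error makes the vaccine look milder. The rule is also out of step with the rest of the SAP. Missing causality counts as related (5.3.1.2), a reaction too large to measure is Grade 3 (4.4.1.1.1), and an unsolicited AE with missing onset stays in the tables (5.3.1.5).

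**Working it through.** **No figure in the plan to reproduce.** The documents give neither an expected solicited-reaction rate nor an expected frequency of missing daily records. The cell size used below, 75 per group and age stratum, is from the Protocol synopsis.

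**Direction, for pain, headache, malaise and myalgia.** Among n subjects with an investigator answer, let a be reactors with daily records and y be subjects with Yes and no daily records. Subjects with No and no daily records are already in n as None.

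- Rate under the SAP: a/(n-y)
- Rate counting every recorded Yes: (a+y)/n
- Difference: (a+y)/n - a/(n-y) = y(n-a-y)/(n(n-y))

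Since a+y cannot exceed n, the difference is never negative. It is zero only if y = 0 or every subject reacted. Enumerating all integer cases with n from 2 to 79 found no exception.

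**Size.** Let p be the true rate and m the fraction of reactors without daily records, so a = np(1-m) and y = npm.

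- Reported rate: p(1-m)/(1-mp)
- Shortfall: mp(1-p)/(1-mp)

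For example, at p = 0.30 and m = 0.10: 0.10 × 0.30 × 0.70 / (1 - 0.03) = 0.021/0.97 = 2.16 points. The values of m are assumptions.

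| True rate p | m = 2% | m = 5% | m = 10% |
|---|---|---|---|
| 10% | 0.18 | 0.45 | 0.91 |
| 30% | 0.42 | 1.07 | 2.16 |
| 50% | 0.51 | 1.28 | 2.63 |
| 70% | 0.43 | 1.09 | 2.26 |
| 80% | 0.33 | 0.83 | 1.74 |

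(Shortfall in percentage points.) It is largest near p = 50% and falls on either side.

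**In whole subjects.** With 45 true reactors among 75, the rate is 60.00%. If 1, 3 or 5 of them have no daily records, the SAP reports 44/74 = 59.46%, 42/72 = 58.33% or 40/70 = 57.14%.

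**Difference between arms.** At m = 10% in both arms, true rates of 50% and 70% become 47.4% and 67.7%, so the gap widens from 20.0 to 20.4 points. True rates of 30% and 50% become 27.8% and 47.4%, so the gap narrows to 19.5. The effect on a contrast has no fixed sign.

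**Measured reactions.** Let r be the rate among subjects with records, and q the share of the y excluded subjects who would have graded at least 1. The error is r - [r(n-y)+qy]/n = (y/n)(r-q), so the SAP rate is too low only if q exceeds r. With n = 75 and y = 3:

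- r = 10%, q = 60%: 0.04 × (0.10 - 0.60) = -2.0 points
- r = 30%, q = 10%: 0.04 × (0.30 - 0.10) = +0.8 points

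Redness and swelling grade from 25 mm, so a Yes can legitimately grade as None. Limb circumference grades from any increase above 0 mm, which makes a high q more likely, but without a measurement it cannot be confirmed.

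**The case against.** The best defence is that the case should be rare. Protocol 13.2 requires verbal clarification of missing diary entries and transfer to the eCRF. Protocol 11.1 has undocumented information captured in source and then entered. The diary is reviewed at V02 (Protocol 9.3.1.3). A No with blank days may also be ordinary data entry, not a lost diary. Even the largest shortfall in the table, 2.6 points, is small against the precision of one cell: the exact 95% interval for 45/75 is about 48% to 71%, and no hypothesis is tested. All of this stands and bears on size. None of it supplies the missing rule, and the shortfall does not depend on how many No subjects there are.

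A reader might infer more than the documents support:

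- **That fever is affected.** It is not. Fever is exempt from step 1, so No and Yes without records are treated alike.
- **That the bias is greatest in the most reactogenic arm and shrinks differences.** The formula peaks near 50%, and gaps can widen.
- **That every solicited rate is pushed down.** For redness, swelling and limb circumference the direction is conditional. Grade-specific rates can rise, because dropping a Grade 1 or 2 reactor shrinks the denominator of the Grade 3 percentage.
- **That a lost record could move ELS across the 3% alert**, for instance from 3/75 = 4.0% to 2/74 = 2.7%. SAP 4.4.1.1.1 treats every instance of ELS as Grade 3, which may already keep a Yes in. The alert is defined on recipients in an early review of preliminary data and is not tied to the 4.4.1.1.3 denominator. ELS also triggers immediate site contact, so an unrecorded case is unlikely.
- **That 4.4.1.1.3 flatly contradicts 5.3.1.** A specific rule sits under a general one, and 5.3.1.4 points to the specific rule. It is a poor fit that should be reconciled.

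**Conclusion.** The concern holds for solicited reactions other than fever. As written, the SAP keeps a No and excludes a Yes when there are no daily records. For pain, headache, malaise and myalgia this can only lower the any-grade D0 to D7 rate. At an assumed m of 2% to 10% the shortfall is about 0.4 to 2.3 points at true rates of 30% or 70%, with a maximum of about 2.6 points near 50%.

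This rests on three assumptions: the investigator's Yes is taken as correct, non-reactors without daily records have a recorded No, and m lies in a range that the documents do not give. The real effect is probably small. Nothing general can be said about which arm is most affected or whether differences between formulations shrink. For measured reactions the direction depends on the unknown sizes, and for ELS the SAP leaves the handling unstated. The correction is worth making because the rule depends on the outcome and is cheap to repair.

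**What to change.** Amend SAP 4.4.1.1.1 and 4.4.1.1.3, and align 5.3.1 with them:

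- **Pain, headache, malaise, myalgia.** Treat an investigator Yes with all daily records missing as present, intensity missing. Count it in numerator and denominator of the any-grade D0 to D7 rate only. A bare Yes cannot be placed in D0 to D3 or D4 to D7, nor in a grade. Report the number of such subjects by study group.
- **ELS.** State explicitly that a Yes without a daily record is counted as present and Grade 3.
- **Redness, swelling, limb circumference.** Show these subjects in a row for reactions reported with size missing, and give a sensitivity rate that counts them as present.
- **Fever.** No change.

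The cost is a short SAP rule, the matching programming and one table row. The presence field is already collected, so no new data are needed. The downside is that some any-grade rates rise slightly.

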4.4.1.1.2 Maximum Overall Intensity

Maximum overall intensity is derived from the daily intensities computed as described in Section [4.4.1.1.1](#) and is calculated as the maximum of the daily intensities over the period considered.

4.4.1.1.3 Presence

Presence is derived from the maximum overall intensity on the period considered:

- None: No presence
- Grade 1, Grade 2, or Grade 3: Presence
- Missing: Missing presence

Subjects with at least one non-missing presence for a specific endpoint will be included in the analysis. Conversely, those without a non-missing presence will not be included in the analysis of the endpoint.

4.4.1.1.4 Time of Onset

Time of onset is derived from the daily intensities computed as described in Section [4.4.1.1.1](#). It corresponds to the first day with intensity of Grade 1, Grade 2, or Grade 3.

Note: If a reaction is not continuous (i.e., reaction occurs over two separate periods of time intervened by at least one daily intensity Missing or None) then the time of onset is the first day of the first occurrence.

4.4.1.1.5 Number of Days of Occurrence

Number of days of occurrence over the period considered is derived from the daily intensities computed as described in [Section 4.4.1.1.1](#). It corresponds to the number of days with daily intensities of Grade 1, Grade 2, or Grade 3. Number of days of occurrence on the solicited period with a specified intensity may also be derived.

4.4.1.1.6 Overall Number of Days of Occurrence

Not applicable.

4.4.1.1.7 Ongoing

Ongoing is derived from the last daily intensity of the solicited period computed as described in [Section 4.4.1.1.1](#) and the maximum intensity on the ongoing period. The investigator's ongoing flag is not used because the measurement would determine the ongoing status of the reaction. Note the intensity could be considered None (not a reaction) in the analysis despite being considered a reaction by the investigator (e.g., swelling measurement > 0 mm but < 25 mm in adults).

If the last daily intensity of the solicited period is at least Grade 1 and maximum intensity on the ongoing period is also at least Grade 1, then the reaction is considered ongoing. In any other cases the reaction will not be considered as ongoing.

4.4.1.2 Unsolicited Non-serious AEs

4.4.1.2.1 Intensity

Intensity for unsolicited non-serious AE will be derived according to the following classification: None, Grade 1, Grade 2, Grade 3, or Missing.

If the unsolicited non-serious AE is measurable and its preferred term is part of the list of solicited reactions, then the measurement is derived based upon and following the same rule than the intensity scales defined in the protocol for that measurable injection site or systemic reaction. Note the intensity could be considered "None" (not a reaction) in the analysis despite being considered a reaction by the investigator (e.g., swelling measurement > 0 mm but < 25 mm in adults).

Intensity for the other unsolicited non-serious AEs will correspond to the value reported in the CRF.

The maximum intensity corresponds to the highest intensity for a unique term.

Note: If a measurable unsolicited non-serious event not matching solicited reactions does not have an intensity reported in the clinical database, then the statistician should work with the clinical team to determine intensity and include the scales in this section. If no scales can be determined, then the intensity should remain missing.

4.4.1.2.2 Last Vaccination

Not applicable, as there is only one vaccination.

4.4.1.2.3 Time of Onset

Time of onset is derived from the start date of the unsolicited non-serious AE provided in the clinical database and the date of last vaccination:

- start date of the unsolicited non-serious AE minus date of previous vaccination

The time of onset should be considered as missing only if one or both of the dates are missing or partially missing.

The unsolicited non-serious AEs will be analyzed “Within 30 days”, which corresponds to AEs with a time of onset between 0 and 30 days after vaccination or missing. An AE with missing time of onset will be considered to have occurred just after the vaccination indicated by the visit number, so will be included in these tables.

Note: Unsolicited non-serious AE that occurred before vaccination (negative time of onset) or with a time of onset will not be included in analysis, but will be listed separately.

